5.8 Exclusion criteria

- Patients with other known causes of proteinuria, e.g. UTI, fever
- At screening visit SBP higher than 160 mmHg or DBP higher than 100 mmHg or SBP lower than 90 mmHg
- Glycated hemoglobin (HbA1C) >11%
- Known hypersensitivity to dapagliflozin or finerenone
- Known case of Addison's disease
- Known case of hepatic insufficiency
- Treatment with SGLT2i (empagliflozin:62 hours, dapagliflozin:65hours) or MRAs (finerenone:10-20 hours, spironolactone:7 hours , eplerenone:15-30 hours) within their wash out periods.
- Patients on non-dihydropyridine Calcium Channel blockers or Glucagon-like peptide-1 (GLP-1) agonists
- Pregnant lady or lactating mother

5.9. Sample size: Sample size calculation for hypothesis testing of difference between two proportions:

$$n = \frac{p(100 - p) + q(100 - q)}{(p - q)^2} (z_{\alpha} + z_{\beta})^2$$

Where,

Z_{α} = Z value of standard normal distribution at a definite level of significance

Z_{β} = Z value of standard normal distribution at a definite level of power

p = Percent change from baseline in UACR after treatment in the experimental group

q = Percent change from baseline in UACR after treatment in the control group

Here,

Z_{α} = 1.96 at 95% Confidence Interval

Z_{β} = 1.28 at 90% power

p = 36% (Mårup et al., 2024)

q = 8% (Mårup et al., 2024)

So,

$$n = \frac{36(100-36) + 8(100-8)}{(36-8)^2} (1.96 + 1.28)^2 \approx 40$$

Considering 10% lost to follow-up final sample will be $(40 + 40 \times 10\%) = 44$. That means 44 patients in each group will be needed to test the hypothesis.

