Evaluation of patients at 4 weeks: The patients will be followed up at 4 weeks. The physical examinations will be done, and the following parameters will be measured at follow-up: Serum creatinine, eGFR, serum potassium, FBS, 2HPPBS, Urine R/E and Urinary ACR. The patients will be instructed to report immediately in case of any adverse events following consumption of the drugs. If a patient develops symptoms or signs suggestive of genital mycotic infection (itching, erythema, discharge), a culture and sensitivity (C/S) test of vaginal discharge (in female) or penile swab (in male) will be performed. Tolerability will be assessed by employing an adverse event profile (adverse events, serious adverse events). Safety will be evaluated based on the incidence of A/E. The safety population consists of subjects who receive at least one dose of study medication. Necessary action will be taken for any adverse effect complained by participants.

Evaluation of patients at 8 weeks and outcome assessment: All the patients will be evaluated at 8 weeks again. Physical examination will be done. Biochemical parameters will be reassessed, including Serum Creatinine, eGFR, Serum Potassium, FBS, 2HPPBS, urine R/E and urinary ACR. If a patient does not return for a scheduled visit, every effort will be made to contact the patient. If possible, every effort will be made to document patient outcomes in any circumstance. The investigator will enquire about the reason for withdrawal, request that the patient return all unused study medication, and ask that the patient return for a final visit, if applicable, and follow up with the patient regarding any unresolved adverse events

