In every visit, for blood test, blood will be collected from accessible vein with proper aseptic precaution and patient remained at least 8 hours overnight fasting before blood collection and blood was collected into red topped vacutainer. After collection of 10 mL blood, it will be allowed to clot by leaving it undisturbed at room temperature for 10-15 minutes and will removed the clot by centrifuging at 3000rpm for 10 minutes for serum. Serum creatinine concentration will be measured by buffer kinetic jaffe reaction using a SIEMENS dimension EXL200 analyzer while eGFR will be measured by CKD-EPI formula. The urinary albumin concentration was determined using a nephelometry method by BN pro-spec analyzer while urinary creatinine concentration was measured by endpoint spectrophotometric method with an alkaline picrate solution using a SIEMENS dimension EXL200 analyzer. UACR will be calculated by dividing the concentration of urinary albumin by the concentration of urinary creatinine. All the investigations will be performed in an ISO certified laboratory.

5.14. Data analysis:

Data will be recorded in the form of an Excel worksheet. After completion of data collection, data will be analyzed using the Statistical Package for Social Sciences (SPSS) version 27.0 (IBM Corp., Armonk, NY, USA). The continuous variables will be presented by measures of central tendency and measures of dispersion. For the normally distributed data, mean \pm standard deviation will be used, and for non-parametric data, median and Interquartile range (IQR) will be presented. On the other hand, we would present the categorical variables as frequency distribution. Between groups, comparisons of independent variables will be performed by independent t-test and Mann-Whitney U-test for normally and not-normally distributed variables respectively. Within patients, comparison will be performed by paired t-test or Wilcoxon Signed Rank Test, as appropriate. The Chi-square test will investigate the differences in categorical variables between two groups. Repeated measures ANOVA will be performed to compare mean values across multiple time points within the same group. Where appropriate, post-hoc analysis with Bonferroni correction will be conducted to identify specific time points with significant difference. A p-value <0.05 will be considered statistically significant.

[figure not shown]

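### Dipstick albumin is an ordered scale, but the plan compares it between arms with a chi-square test that ignores the order

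*Protocol*

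**What the plan says.** The biochemical variables table in protocol section 5.10 lists urinalysis albumin as categorical, on a six-grade scale from negative through trace to four plus, to be shown as frequencies. Section 5.13 has routine urine examination done at baseline and at both follow-up visits; the week-4 list includes "FBS, 2HPPBS, Urine R/E and Urinary ACR", and week 8 repeats it.

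Section 5.14 gives one rule for categorical variables: "The Chi-square test will investigate the differences in categorical variables between two groups". It makes no exception for ordered categories. The rank test appears in another sentence, as part of the pair "independent t-test and Mann-Whitney U-test for normally and not-normally distributed variables respectively". The significance threshold is "A p-value <0.05 will be considered statistically significant".

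The dipstick has no further role in the plan. The primary outcome is change in UACR, none of the five specific objectives in 4.2 names the dipstick, and it does not enter the sample size in 5.9.

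**The concern.** Pearson's chi-square statistic does not change when the columns of the table are rearranged. Applied to the six grades, it has 5 degrees of freedom and spreads its power over every kind of difference between arms, including patterns with no net movement up or down. The research hypothesis in 3.2 is directional: the combination lowers albuminuria more. For an ordered measure of albuminuria, the difference of interest is therefore a shift along the scale, and a rank or trend test puts its single degree of freedom there.

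Little is at stake, but something is. Dipstick albumin is the only recorded measure of albuminuria besides UACR. Under the rule as written, a moderate shift in grades could well be missed, and a significant result would not by itself show the direction of the difference.

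**Working it through.** **The plan's own figure.** Section 5.9 uses "1.96 at 95% Confidence Interval" and "1.28 at 90% power", with 36% and 8%:

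n = [36×64 + 8×92] / 28² × (1.96 + 1.28)² = 3040/784 × 10.4976 = 40.7.

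The protocol states 40, and 40 × 1.10 = 44: "44 patients in each group will be needed to test the hypothesis". The figure reproduces to within rounding. It concerns UACR; the protocol gives no power figure for the dipstick. The checks below use 40 (evaluable) and 44 (enrolled) per arm and a two-sided 5% level.

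**Why order matters.** With equal arms, the expected count in each cell is half the column total, so X² = Σ (c − t)²/(c + t), where c and t are the control and combination counts in a grade. Two invented tables with 40 per arm and four grades scored 1 to 4:

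- Table A: control 6, 8, 12, 14; combination 14, 12, 8, 6. X² = 64/20 + 16/20 + 16/20 + 64/20 = 8.0 on 3 df, p = 0.046. Mean grades are 114/40 = 2.85 and 86/40 = 2.15, a difference of 0.70.
- Table B: the same columns in another order, control 6, 14, 12, 8; combination 14, 6, 8, 12. X² is again 8.0, p = 0.046. Mean grades are 102/40 = 2.55 and 98/40 = 2.45, a difference of 0.10.

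The linear-by-linear statistic is (N − 1)r². Each grade holds 20 of 80 patients, so the score variance is 1.25 and r² = difference² × 0.25/1.25 = 0.2 × difference².

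- A: 79 × 0.2 × 0.49 = 7.74, p = 0.005.
- B: 79 × 0.2 × 0.01 = 0.16, p = 0.69.

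Chi-square cannot tell the two tables apart; the trend test can.

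**Power at equal noncentrality.** Power is P(χ²_k(λ) > the 95% point of χ²_k).

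| λ | 1 df | 3 df (four grades) | 5 df (six grades) |
|---|---|---|---|
| 3.84 | 50% | 34.5% | 28.1% |
| 7.85 | 80% | 64.5% | 55.5% |
| 10.51 | 90% | 78.4% | 70.3% |

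At 80%, the shortfall is 24.5 points with six grades and 15.5 points with four.

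**Simulation, proportional-odds shift, 44 per arm, six grades.** Three control distributions were assumed, because the protocol gives none: (.05, .10, .25, .30, .22, .08), uniform, and (.02, .05, .15, .28, .32, .18).

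| Odds ratio | Chi-square | Mann-Whitney or trend |
|---|---|---|
| 2.0 | 21–23% | 42–45% |
| 2.5 | 36–41% | 65–67% |
| 3.0 | 54–56% | 81–82% |
| 4.0 | 78–80% | 95% |

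Over these odds ratios and 40 to 44 per arm, the shortfall is about 15 to 29 points. With four grades in use it is about 9 to 18 points. With no true effect, chi-square rejects in about 4–5% of tables and the ordinal tests in about 5%. With the two unequal distributions, over 99% of tables have an expected count below 5, yet the type I error holds. The problem is efficiency, not false positives.

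**A shift borrowed from UACR.** If the 36% and 8% are read as falls in UACR, the ratio is 0.64/0.92 and the log difference is ln(0.92/0.64) = 0.363. Dividing by an assumed SD of log UACR gives the latent shift, here with 40 per arm and six grades:

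| Assumed SD | Shift (SD) | Chi-square | Mann-Whitney | Shortfall |
|---|---|---|---|---|
| 0.5 | 0.73 | 60–61% | 85–86% | 24–25 points |
| 0.8 | 0.45 | 24–27% | 47–48% | 21–23 points |
| 1.5 | 0.24 | 9% | 17% | 8–9 points |

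For larger shifts the gap closes: 13 to 14 points at 0.9 SD and 4 to 5 points at 1.1 SD.

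**The case against.** The strongest reply is that the dipstick is one item of routine urinalysis, to be shown as frequencies, and that no section plans a named between-arm test of it. The test is inferred by joining the variable list to a general sentence. The categorical outcome that is an objective, a UACR fall of at least 30%, is binary and suits chi-square, as do the yes/no adverse events. The choice of test for such an item could also be left to a statistical analysis plan, and SPSS prints the linear-by-linear statistic beside chi-square anyway.

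Most of this stands, and it sets the rank of the point. It does not remove it: 5.14 states a rule rather than staying silent, and the rule fits this variable badly.

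A reader might infer more than the documents support:

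- **A fixed fraction of power lost.** There is none. At an odds ratio of 2 the relative loss is about half (22% against 43.5% at mid-range); at 3 it is about a third (55% against 81.5%). For very large shifts it falls to about 4–5%.
- **An expected dipstick shift.** The 36% and 8% in 5.9 are UACR changes.
- **A bar on the rank test.** Section 5.14 speaks of variables that are not normally distributed and does not say continuous. The routing to chi-square comes from the categorical label in 5.10.
- **A clash with UACR.** Nothing in the protocol makes the dipstick a check on the primary result or says that a non-significant dipstick comparison would be read against it.

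**Conclusion.** The point holds as a minor one. Read together, 5.10 and 5.14 assign an ordered six-grade scale to a test that ignores order. The cost is about 15 to 29 percentage points of power with six grades in use and about 9 to 18 with four, at about the same 5% type I error. These figures assume a one-directional proportional-odds shift with an odds ratio of 2 to 4, 40 to 44 patients per arm, and grade distributions that the protocol does not give. A weaker or much stronger shift narrows the gap in points. The primary UACR analysis, the specific objectives and the sample size do not depend on this choice.

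**What to change.** In 5.10, list urinalysis albumin as ordinal. In 5.14, keep chi-square for binary and unordered categories, and add one sentence: dipstick albumin is compared between arms at weeks 4 and 8 with the Mann-Whitney test or the linear-by-linear association test (name one in advance), reporting a common odds ratio or the probability of a lower grade with its 95% CI. The frequency table stays as planned.

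The cost is one word and one sentence, with no new data, visits, patients or software. The benefit is equally modest, since it is confined to a supportive variable.

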To evaluate the effect of dapagliflozin-finerenone combination on albuminuria in patients with chronic kidney disease and type 2 diabetes compared to dapagliflozin alone.

4.2 Specific Objectives:

1. To compare the change in urinary albumin-to-creatinine ratio (UACR) from baseline to the end of the study between dapagliflozin - finerenone combination group and dapagliflozin alone group.
2. To compare the changes in serum potassium levels between the two groups during the study period.
3. To estimate and compare the changes of eGFR between the two groups.
4. To evaluate the proportion of patients achieving a clinically significant reduction in albuminuria (e.g., $\geq 30\%$ decrease in UACR) in each groups.
5. To evaluate the overall safety and tolerability profiles of the combination therapy compared to dapagliflozin monotherapy.

5. Materials and method:

5.1. Type of study: Randomized, open-label, active controlled trial.

5.2 Place of Study: Department of Nephrology, Medicine and Endocrinology & Metabolism, Chittagong Medical College Hospital, Chattogram, Bangladesh.

5.3 Study period: One and half year from acceptance of protocol.

5.4 Study population: Adults with chronic kidney disease and type 2 diabetes attending the Nephrology, Medicine and Endocrinology & Metabolism outdoors at CMCH will be the study population during the study period.

5.5 Study groups: Based on the interventions, there will be two groups in the study

1. Experimental group: Dapagliflozin 10 mg plus finerenone 10 mg
2. Control group : Dapagliflozin 10 mg alone

5.6 Sampling technique: Consecutive patients attending the Nephrology, Medicine and Endocrinology & Metabolism Departments at CMCH will undergo screening based on predefined inclusion and exclusion criteria. Eligible participants will be randomly allocated (via computer-generated randomization) to one of the two treatment arms.

5.7 Inclusion criteria:

- Patients aged ≥ 18 years
- Patients with T2 DM , as defined by the American Diabetic Association.
- Urinary ACR ≥ 30 mg/g and eGFR ≥ 25 ml/min per 1.73 m²
- Prior treatment with ACEIs or ARBs for more than four weeks up to the maximum tolerated dose
- Serum potassium ≤ 4.8 mmol/L

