5.15. The utilization of results: This trial will provide critical evidence on the efficacy and safety of dapagliflozin-finenone combination in a resource-limited setting, addressing a significant unmet need in the management of DN. Every effort will be made to publish the results in peer-reviewed national and international journals. The results of this study will be published as a thesis and submitted to the corresponding university as MD (Nephrology) exam requirement. The result of the study will be presented to the Department of Nephrology, CMCH.

5.16. Ethical Implication: The study will be conducted after the approval of the Ethical Review Committee of Chittagong Medical College. Voluntary written consent will be taken from the patient and legal guardians. All measures will be taken to protect anonymity. The interviews of the patient, clinical examination and investigations will be performed at the respective hospital after explaining the nature and purpose of the study to them, assuring that the information given by them will be used for the interest of the community and that the particulars of the patients will not be disclosed anyway.

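### For adverse events the protocol states no between-arm inference beyond a chi-square test at p<0.05, and at 44 per arm that cannot show how large an excess of hyperkalaemia remains possible

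*Protocol*

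**What the plan says.** - **Objective.** Section 4.2, objective 5, is comparative: "To evaluate the overall safety and tolerability profiles of the combination therapy compared to dapagliflozin monotherapy". Objectives 2 and 3 compare changes in serum potassium and eGFR between the arms.
- **Basis of the safety evaluation.** Section 5.13 (evaluation at 4 weeks) says "Safety will be evaluated based on the incidence of A/E" and defines a safety population of everyone who takes at least one dose. Section 5.10 lists adverse events as present or absent, shown as frequency (%).
- **Analysis.** For categorical variables, section 5.14 says "The Chi-square test will investigate the differences in categorical variables between two groups". It sets one criterion for all tests: "A p-value <0.05 will be considered statistically significant". Continuous variables are compared by t-test or Mann-Whitney test. The section mentions no between-arm risk difference, mean difference or confidence interval.
- **Sample size.** Section 5.9 uses "1.96 at 95% Confidence Interval" and "1.28 at 90% power", with UACR inputs only, and arrives at 44 per arm.
- **Use of the result.** Section 5.15 says "This trial will provide critical evidence on the efficacy and safety of dapagliflozin-finenone combination in a resource-limited setting". The conclusion of the Part C Summary likewise promises to clarify safety.

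**The concern.** Section 5.11 G names hyperkalaemia as finerenone's most common adverse event, and the Introduction wants the findings to help weigh albuminuria benefit against hyperkalaemia and eGFR change. That weighing needs an estimate of the extra risk and its uncertainty. The stated analysis supplies a frequency per arm and a p-value. At this sample size a real excess of several percentage points will often give p≥0.05, and nothing in the planned output would show the reader that such an excess is still compatible with the data.

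**Working it through.** **1. The plan's own size (section 5.9).** [36×64 + 8×92]/(36−8)² × (1.96+1.28)² = (2304+736)/784 × 10.4976 = 40.7, stated as 40; 40 + 10% = 44. The figure reproduces to rounding. Both inputs concern UACR, and no safety outcome enters.

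**2. Chance of missing a true excess of hyperkalaemia.** The event rates are assumptions, because the protocol gives none. The test is the uncorrected Pearson chi-square at two-sided 5% (two-sided because section 5.9 uses 1.96). For each pair of true rates, the binomial probabilities of all outcomes with chi-square ≤ 3.84 are summed. The 40-per-arm column is the section 5.9 number before the loss allowance.

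| Control v combination | Excess (points) | Missed, 44 per arm | Missed, 40 per arm |
|---|---|---|---|
| 5% v 10% | 5 | 84% | 85% |
| 2% v 10% | 8 | 62% | 66% |
| 5% v 15% | 10 | 62% | 65% |
| 10% v 20% | 10 | 73% | 75% |
| 2% v 12% | 10 | 49% | 54% |
| 2% v 15% | 13 | 32% | 37% |
| 2% v 20% | 18 | 13% | 17% |
| 5% v 25% | 20 | 20% | 24% |

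For an excess of 5 to 10 points, the miss rate at 44 per arm is 62% to 84% in most of these pairs. It falls to about one half in the most favourable one (2% v 12%). By the normal approximation, 80% power at 44 per arm needs a combination rate of about 21% against 2%, or 27% against 5%.

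**3. The chi-square at these counts.** With six events in all, the expected count is 6×44/88 = 3 per arm, below the usual minimum of 5. Fisher's exact test would then be more appropriate, and it misses more. At 44 per arm its power is 14% for 2% v 10%, 22% for 5% v 15% and 5% for 5% v 10%.

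**4. What a p-value hides: 5/44 v 1/44.**
- Chi-square = 88×(5×43 − 1×39)²/(44×44×6×82) = 2.86, p = 0.09. Fisher p = 0.20.
- Risk difference = 0.114 − 0.023 = 0.091.
- Wilson limits are 0.050 to 0.240 (combination) and 0.004 to 0.118 (control).
- Newcombe lower limit: 0.091 − √[(0.114−0.050)² + (0.118−0.023)²] = −0.024.
- Newcombe upper limit: 0.091 + √[(0.240−0.114)² + (0.023−0.004)²] = 0.218.

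The 95% CI therefore runs from −2 to +22 points. Even with no event in 44 patients, the one-sided 95% upper bound on the rate is 1 − 0.05^(1/44) = 6.6%.

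**5. Continuous safety variables.** A two-sample t-test misses a difference of 0.5 SD in potassium or eGFR change 36% of the time at 44 per arm (40% at 40). With an assumed SD of 0.5 mmol/L, power for a 0.3 mmol/L mean difference in potassium is about 80%.

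**The case against.** The strongest reply is that the protocol commits no stated error. The chi-square sentence is a general line for all categorical variables, and the sentence on how safety is judged names incidence, not a test. Incidences by arm are reported, potassium is also compared as a continuous change, and the monitoring appendix records each event with severity and relatedness. A 5 v 1 imbalance would be visible whatever its p-value. Low power for adverse events is normal in a trial sized for efficacy, and intervals may be specified in an analysis plan that is not at hand.

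Much of this stands. A reader might infer that the protocol will treat p≥0.05 as proof of safety, or that the p-value is the sole source of safety information. The documents support neither: no such rule is written, and the descriptive and continuous results exist alongside the test. It would also be too strong to say that the test misses most relevant excesses. The protocol gives neither event rates nor a relevant excess, and differences near 20 points are usually detected. No safety margin is owed, because no equivalence or non-inferiority claim is made.

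What does not fall away is that section 5.14 already selects the between-arm inference, while objective 5 and section 5.15 already promise a comparative result. Frequencies without an interval carry no measure of uncertainty, and a mean potassium difference does not say how many patients become hyperkalaemic. One further limit is fair: the hyperkalaemia item in the case record form is a bare yes/no with no threshold beside it, so any interval is only as clear as that definition.

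**Conclusion.** The point holds as a mismatch between the safety result promised and the inference stated for it. At 44 per arm, the chi-square test misses the assumed hyperkalaemia excesses of 2% v 10%, 5% v 15% and 5% v 10% in 62%, 62% and 84% of trials. The size depends on those assumed rates: at 2% v 12% it is 49%, and for 2% v 20% and 5% v 25% it is 13% and 20%. A non-significant result could not by itself support a statement that the combination is as safe as dapagliflozin alone, although the protocol does not say that it would be used that way. This is a worthwhile, inexpensive improvement to the reporting of safety. It does not call the UACR comparison into question and is no reason to enlarge the trial.

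**What to change.** In section 5.14:

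- For hyperkalaemia and each other adverse event, report the between-arm risk difference with a 95% CI (Newcombe or exact), in the safety population defined in section 5.13.
- For change in potassium and eGFR, report the between-arm mean difference with a 95% CI.
- Use an exact test instead of chi-square where expected counts fall below 5. This lowers power further, so the interval should carry the interpretation.
- State that a non-significant result will not be reported as showing that the combination is as safe as dapagliflozin alone.

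As a secondary step, soften the safety wording in section 5.15 and in the Summary conclusion to match the precision available.

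The cost is a few sentences, with no extra patients, visits or data. The downside is that the intervals will be wide and the safety statement less favourable.
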